A Randomized Trial to Determine if a Pre-operative Wash With a Chlorhexidine Gluconate Cloth and Chlorhexidine Gluconate Vaginal Scrub Reduces Infectious Morbidity in Patients Undergoing Cesarean Section After Labor

PI: [name]

NCT03423147

Document Date: 3-11-2022

PRACTICAL STUDY **Protocol from Ideate**

Title

A randomized trial to determine if a pre-operative wash with a chlorhexidine cloth and chlorhexidine vaginal scrub reduces infectious morbidity in patients undergoing cesarean section after labor

PI

[name]

Primary Dept

Obstetrics/Gynecology

Application Initiated By

[name]

Lay Summary

Surgical site infections are the second most common cause of infections accounting for 15% of all infections among hospitalized patients and 38% of infections in patients undergoing surgery. In obstetric patients, surgical site infections occur in 5-10% of cesarean sections, which is a higher rate than seen in vaginal deliveries.

Additionally, infections are thought to be highest in those patients who have cesarean sections after undergoing labor.

Chlorhexidine is a chemical antiseptic that reduces bacteria found on the skin but it is not clear if it decreases the risk of surgical site infections.

Historically, chlorhexidine has been studied and used in orthopedic and cardiac implant surgeries. Research on the use of chlorhexidine for SSI prevention in cesarean sections is limited. This study intends to evaluate the effectiveness of use of both chlorhexidine gluconate (CHG) wipe and vaginal scrub in reducing SSI in patients undergoing cesarean section that have previously been laboring. Patients will be randomized to one of two groups: wash with both a pre-operative CHG cloth and vaginal scrub prior to surgery (in addition to standard preoperative scrub) and standard preoperative scrub.

Objective

The objective of this study is to determine if the rate of infectious morbidity is reduced with the use of chlorhexidine gluconate cloths and chlorhexidine vaginal scrub prior to cesarean section in patients previously undergoing labor.

Background

Surgical site infections (SSI) are the second most common cause of nosocomial infections accounting for 15% of all nosocomial infections among hospitalized patients and 38% of nosocomial infections in surgical patients. In obstetric patients, infectious morbidity (i.e. SSI, endometritis) occurs in 5-10% of cesarean sections, which is 5-fold higher than vaginal deliveries. Additionally, infectious morbidity is thought to be highest in those patients who have cesarean sections after undergoing labor.

Chlorhexidine, chemical antiseptic effective on gram positive and gram negative bacteria, reduces skin microflora/colonization but it is not clear if it decreases the risk of SSI.

Historically, chlorhexidine has been studied and used in orthopedic and cardiac implant surgeries. Research on the use of chlorhexidine for SSI prevention in cesarean sections is limited. This study intends to evaluate the effectiveness of use of both chlorhexidine gluconate (CHG) wipe and vaginal scrub with betadyne in reducing SSI in patients undergoing cesarean section that have previously been laboring. Patients will be randomized to one of two groups: wash with a pre-operative CHG cloth and chlorhexidine scrub prior to surgery (in addition to standard preoperative scrub) and standard preoperative scrub.

Primary and Secondary Study Endpoints

The primary outcome will be SSI and postpartum endometritis. Secondary outcomes include other maternal complications or interventions, neonatal ICU admissions, maternal length of stay or readmissions.

Subjects

800

Specify Other Setting of Human Research

Mount Sinai Hospital labor and delivery floor

Feasibility of Meeting Recruitment Goals

Researchers will have access to all patients scheduled for delivery at Mount Sinai Medical Center. About 1800 deliveries by cesarean section occur each year at Mount Sinai. Of these, approximately 800 are cesarean sections after failed labor. Assuming a primary outcome rate of 20% in the control arm, a sample size of 329 in each group would give 80% power to detect a 40% reduction in surgical site infection between the active group and control. We aim to recruit 400 patients per group (for a total of 800 patients) to account for patient drop out or non-compliance.

Due to the amount of deliveries and volume, we anticipate these recruitment goals to be feasible.

Facilities to Be Used for Conducting Research

Labor and Delivery floor at Mount Sinai Hospital

Inclusion Criteria

The study will be offered to women at > 24 weeks gestation who are admitted in labor or admitted for induction of labor at Mount Sinai Hospital.

Exclusion Criteria

Exclusion criteria include allergy to chlorhexidine, and unplanned or emergency cesarean section.

Other Aspects that Could Increase Subjects Vulnerability

The risks to subjects are inherent to the labor process itself outside of the study. The only difference in care is the use of a 2% chlorhexidine wipe and vaginal scrub in addition to standard preoperative preparation. This may potentially decrease the risk of surgical site infection in women who undergo cesarean section after labor. The only inherent risk of using the wipe and scrub is allergy to 2% chlorhexidine gluconate and this population will be screened by the provider consenting the patient for participation and excluded accordingly.

The patients in our study are all laboring women. All women in this study will have access to labor analgesia as requested by the patient. In addition, enrollment in this study will not alter the current strategies regarding labor analgesia or labor protocols.

Safeguard to protect subjects rights and welfare

There is always the risk of loss of confidentiality; however, there are procedures in place to minimize this risk. To ensure confidentiality, the following system will be adhered to: when subjects are enrolled in this study, they will be assigned a unique identification code. Corresponding medical record numbers for each code (keycode) will be stored in a password locked document on the MFM server that can be accessed only by members of the research team. At the conclusion of the data extraction, the outcome variable will be assessed and the key codes to the medical record numbers will no longer be necessary and that information will be permanently erased from the keycode file. Electronic data with identifiers will be encrypted according to Data Security Standards.

Duration of an individual subjects participation in the study

After informed consent has been obtained, the duration of the subject participation will occur from the time they are admitted until 6 weeks post procedure.

Duration Anticipated to Enroll all study subjects

We expect to enroll patients over a two-year period. We will allow an additional 6 months to perform data analysis.

Procedures for subjects to request withdrawal

A patient may request to withdraw from the study at any time by notifying their obstetric provider.

Procedures for Investigator to Withdraw subjects

The only occasion whereby a subject may be withdrawn is when the cesarean delivery suddenly needs to be performed in an urgent manner.

How Participants will be identified

Patients presenting to labor and delivery for admission for labor will be identified.

How Research will be introduced to participants ***

The study personnel on the labor floor will present the study to the patient in addition to consenting the patient for routine admission for labor and delivery.

Women who are in early labor, in addition to being induced for labor, will be approached by study personnel. Women who are actively delivering will not be approached or included in the study.

How Participants will be screened

The participants will be screened according to the previously mentioned inclusion criteria. The participants will either be screened by obstetrical providers (residents, midwives, physician assistants) who work regularly on the labor floor at the time of admission or a research coordinator/medical student who is under the training of an obstetrical provider for consideration of participation to the study.

All research-related discussions will be held in the patient's private room. Any questions will be answered and fully discussed to maximize patient comfort. If they meet eligibility criteria and chose to participate they will be randomized and receive care within the accepted standards. The electronic medical records will be used for patient information.

Risks to Subjects

The risks to subjects are inherent to the cesarean section process itself outside of the study. The only difference in care is use of chlorhexidine gluconate in one arm of the study. This may result in a decreased rate of infectious morbidity.

If used as instructed, the only potential unforeseeable risk is an allergic reaction to the chlorhexidine gluconate. Allergic reaction could include itching or hives, swelling in the face or hands, swelling or tingling in the mouth or throat, chest tightness, and/or trouble breathing.

The patients in our study are all consented to possible cesarean section upon admission for various indications. The inherent nature of cesarean section requires an abdominal surgery. As standard of care, all women in this study will be provided with analgesia. In addition, enrollment in this study will not alter the current strategies regarding cesarean section.

Description of Procedures taken to lessen the probability of magnitude of risks

There is always the risk of loss of confidentiality; however, there are procedures in place to minimize this risk. To ensure confidentiality, the following system will be adhered to: When subjects are enrolled in this study, they will be assigned a unique identification code. Corresponding medical record numbers for each code (key code) will be stored in a password locked document on the maternal-fetal medicine (MFM) server that can be accessed only by members of the research team. At the conclusion of the data extraction, the outcome variable will be assessed and the key codes to the medical record numbers will no longer be necessary and that information will be permanently erased from the key code file. Electronic data with identifiers will be encrypted according to Data Security Standards.

Provisions for Research Related Harm / Injury

The patients will receive standard obstetric care and have access to the obstetric staff (physicians, nursing) as well as all of the resources on the labor floor including the use of the operating room, blood bank, and continuous fetal

monitoring. Any potential adverse events are inherent to the operative delivery itself and regardless of the study. Any complications that occur during cesarean section will be managed by the obstetricians and anesthesiologists. As standard of care, a physician is present during a cesarean section and is experienced in managing complications. The patient is billed as per standard scheduled cesarean section regardless of complications due to the surgery.

Expected Direct Benefit to Subjects

Direct benefit to subject is unknown. However, the potential benefit is that we may find a reduction in infectious morbidity related to cesarean section.

Benefit to Society

Direct benefit to society is unknown. However, the potential benefit is that we may find a reduction in infectious morbidity related to the cesarean section surgery which may reduce subsequent healthcare costs due to decreased readmissions for surgical site infections.

Provisions to Protect the Privacy Interests of Subjects ***

The patients will be approached upon admission to the labor and delivery floor by a physician. Their participation will not require any additional examinations. All research-related discussions will be held in a private location. Any questions will be answered and fully discussed to maximize patient comfort. If they choose to participate they will be randomized and receive care within the accepted standards. If a patient must be called to find out how the wound is healing, the research team members placing the call will not leave a message or speak to anyone except the patient herself. When called, she will be asked if she can discuss the research study at that time, ensuring patient privacy and comfort.

Economic Impact on Subjects

There are no foreseeable costs that subjects may incur through participation in the research.

Data for Assessing Potential Risks to Pregnant Women and Fetuses

The risks to pregnant women and fetuses are inherent to the cesarean section process itself outside of the study. The only difference in care is use of chlorhexidine gluconate in one arm of the study. This may result in a decreased rate of infectious morbidity.

If used as instructed, the only potential unforeseeable risk is an allergic reaction to the chlorhexidine gluconate. Allergic reaction could include itching or hives, swelling in the face or hands, swelling or tingling in the mouth or throat, chest tightness, and/or trouble breathing.

Description of the study design

This is a prospective randomized trial.

The study will be offered to women who are admitted to Mount Sinai Medical Center to undergo labor. The eligible women will be randomized to use of a 2% chlorhexidine gluconate (CHG) cloth and vaginal scrub (in addition to standard preoperative scrub) or standard preoperative scrub alone. Participants will not be blinded to the arm in which they have been assigned. This study intends to show that the use of chlorhexidine cloth and vaginal scrub prior to cesarean section will reduce the rate of SSI in women who have previously been laboring.

Researchers will have access to all patients scheduled for delivery at Mount Sinai Medical Center. About 1800 deliveries by cesarean section occur each year at Mount Sinai. Of these, approximately 800 are cesarean sections after failed labor. Assuming a primary outcome rate of 20% in the control arm, a sample size of 329 in each group would give 80% power to detect a 40% reduction in surgical site infection between the active group and control. We aim to recruit 400 patients per group (for a total of 800 patients) to account for patient drop out or non-compliance.

Description of Procedures Being Performed

This study intends to evaluate the effectiveness of a chlorhexidine gluconate (CHG) cloth and vaginal scrub in reducing SSI in patients undergoing cesarean section who have previously been laboring. Patients will be randomized to one of two groups: administration of a 2% CHG cloth and vaginal scrub (in addition to standard preoperative care) prior to cesarean delivery or standard preoperative care.

Description of the Source Records that Will Be Used to Collect Data about Subjects

All data will be extracted from electronic medical records (EMR) and phone calls made to subjects if they do not present for their postpartum visit.

Description of Data that Will Be Collected Including Long-Term Follow-Up

Data that will be collected from the EMR include maternal demographics (age, race, BMI, parity) as well as outcomes including surgical site infection and postpartum endometritis. In addition data will be collected regarding other outcomes including maternal complications or interventions, neonatal ICU admissions, maternal length of stay or readmissions. This data collection will start from time of enrollment to 6 weeks postpartum.

Where and When Consent Will Be Obtained

Consent will be obtained upon admission to the labor and delivery floor at Mount Sinai Hospital.

Waiting Period for Obtaining Consent

The patient can be approached and consented starting from admission to labor and delivery and can still be consented to participate in the study at a later time in labor if not already delivered by cesarean section.

Description of Health Information That Will Be Viewed, Recorded, or Generated

Health information collected will include maternal age, parity, gestational age, medical problems, number of previous cesarean sections, indication for cesarean section, time from incision to delivery, type of anesthetic, type and use of prophylactic antibiotics and type of wound closure. Maternal outcomes including estimated blood loss (EBL) will be reviewed. Charts will be reviewed through the 6 week postpartum visit in order to determine how well the skin at the incision site is healing. If patients do not visit Mount Sinai Medical Center for their 2 week wound check, they will be called and asked the following questions: Were you treated for wound infection? Did you experience wound separation or any other wound complications?

Description of Non-Health Information That Will Be Viewed or Recorded

Data collected will include demographic variables such as age, parity, body mass index (BMI) and race.

How PHI Will Be Protected from Improper Use or Disclosure

No specimens will be sent out or received in this trial.

All data is de-identified; patients are followed by subject number. Identifiable patient information (consent forms & consent documentation) are kept separately from any data collected. All consent documentation is stored in a locked cabinet at [REDACTED]. Identifiable enrollment statistics are kept in a password-protected computer (Excel) spreadsheet that is only accessible by members of the research team on a departmental J Drive.

When and How PHI Will Be Destroyed

The key code and data points will be destroyed 7 years after data analysis is complete.

Description of PHI that Will Be Shared

PHI that will be shared will include maternal demographics and maternal outcomes as previously described. Maternal demographics and information collected will include age, parity, BMI, race, gestational age, and number of previous cesarean sections. Additional information will be recorded and shared including time from incision to delivery, type of anesthetic, antibiotic use, type of wound closure, and EBL. Charts will be reviewed through the 6 week postpartum visit in order to determine how well the skin at the incision site is healing.

Justification for Sharing PHI

The PHI will be shared for means of data analysis by members of the research team and statisticians.

With Whom Directly PHI Will Be Shared

The PHI will be shared with members of the research team

Location Where Data Will Be Stored

All research data will be stored in a password-protected database maintained on a secure network drive on the hospital server.

Duration Data Will Be Stored

The key code and data points will be destroyed 7 years after analysis is complete.

Steps That Will Be Taken to Secure the Data During Storage, Use, and Transmission

To minimize risk of loss of confidentiality, study subjects will be assigned a unique identification code. The unique ID code will be linked to the subject's medical record number. The linking key code will be encrypted and stored separately on a secure excel spreadsheet accessible only by the PI and research staff. All research data will be stored in a password-protected database maintained on a secure network drive on the hospital server.

Steps That Will Be Taken to Secure the Data During Storage, Use, and Transmission

To minimize risk of loss of confidentiality, study subjects will be assigned a unique identification code. The unique ID code will be linked to the subject's medical record number. The linking key code will be encrypted and stored separately on a secure excel spreadsheet accessible only by the PI and research staff. All research data will be stored in a password-protected database maintained on a secure network drive on the hospital server.

Data Analysis Plan Including Any Statistical Procedures

Data will be analyzed on an intention to treat basis. Statistical analysis will be performed by SAS using X 2 test or Fisher exact test (categorical variables) and student t test or Mann-Whitney U test (continuous variables). Statistical significance will be set at $p<0.05$.

Study Fund Account (or alternate departmental / fund account, if study is not yet established)
[REDACTED]

Generic Name

4% chlorhexidine gluconate

Brand Name

BD E-Z Scrub 107 Surgical Scrub Brush/Sponge 4% Chlorhexidine-Gluconate

IND Number

[REDACTED]

Name of IND Holder

[name]

Drug / Biologic Description (Manufacturer/Generic Name/Form/Strength)

Drug: BD E-Z Scrub 107 Surgical Scrub Brush/Sponge 4% Chlorhexidine-Gluconate

Biologic Description: Antiseptic

Manufacturer: Becton, Dickinson and Company

Generic Name: 4% chlorhexidine gluconate

Form: Scrub Brush/Sponge

Strength: 4% chlorhexidine gluconate w/v

Effective Date: 3/11/2022

End Date: 3/10/2023

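### Do a single mention of betadyne and an unlabelled 4% product leave the vaginal scrub, and so the tested intervention, undefined?

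*Combined protocol and SAP*

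**What the plan says.** The combined protocol and SAP describes the active arm in several places.

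- **Title:** the trial asks whether a "pre-operative wash with a chlorhexidine cloth and chlorhexidine vaginal scrub reduces infectious morbidity". The cover title says the same with the full chemical name.
- **Objective:** whether infectious morbidity is "reduced with the use of chlorhexidine gluconate cloths and chlorhexidine vaginal scrub prior to cesarean section".
- **Lay Summary:** the study evaluates the "use of both chlorhexidine gluconate (CHG) wipe and vaginal scrub in reducing SSI in patients undergoing cesarean section".
- **Background:** the corresponding sentence reads "chlorhexidine gluconate (CHG) wipe and vaginal scrub with betadyne in reducing SSI in patients undergoing cesarean section". The next sentence assigns the active group a "wash with a pre-operative CHG cloth and chlorhexidine scrub prior to surgery (in addition to standard preoperative scrub").
- **Other Aspects that Could Increase Subjects Vulnerability:** "The only difference in care is the use of a 2% chlorhexidine wipe and vaginal scrub in addition to standard preoperative preparation", and then "The only inherent risk of using the wipe and scrub is allergy to 2% chlorhexidine gluconate".
- **Risks to Subjects, and Data for Assessing Potential Risks to Pregnant Women and Fetuses:** both state that the arms differ only in that one of them receives chlorhexidine gluconate.
- **Exclusion Criteria:** "Exclusion criteria include allergy to chlorhexidine, and unplanned or emergency cesarean section".
- **Drug / Biologic Description:** one product is listed, a surgical scrub brush or sponge with 4% w/v chlorhexidine gluconate. The section does not say whether this is the vaginal scrub. No product is listed for the cloth.

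**The concern.** The vaginal scrub is one of the two components that separate the arms. If the protocol named two different antiseptics for it, a reader could not say what the trial tests, and the result could not be tied to a defined intervention. If betadyne were truly part of the active arm, an exclusion that names only chlorhexidine allergy, and the statements that chlorhexidine is the sole difference between arms, would not describe that arm.

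The strength raises a similar question. A 2% figure attached to both wipe and scrub, beside a single listed product at 4%, looks like a direct contradiction. The section on procedures, where one would look for the answer, gives no separate agent or strength for the scrub.

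**Working it through.** **Agent.** The study scrub is mentioned 13 times:

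| How the scrub is described | Where | Count |
|---|---|---|
| Chlorhexidine attached directly to the scrub | Cover title, Title, Objective, arm sentence in Background | 4 |
| Chlorhexidine before the wipe or cloth, followed by the vaginal scrub | Lay Summary (2), Other Aspects (1), study design (2), procedures (2) | 7 |
| Wipe and scrub tied together to chlorhexidine allergy | Other Aspects | 1 |
| Betadyne | Background | 1 |

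4 + 7 + 1 + 1 = 13. In the first row, the Background arm sentence omits the word vaginal, so three of the four are explicit and one is clear from context.

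The most telling comparison is between the Lay Summary and Background sentences. They are almost the same sentence, and the reference to betadyne is the notable difference. The sentence that follows in the Background, which defines the arms, goes back to chlorhexidine. All three statements on the sole difference in care name chlorhexidine, and none names betadyne.

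**Strength.** The same 13 mentions divide as follows: 9 give no strength, 3 put 2% before the wipe or cloth (and can be read as describing that item alone), 1 applies 2% to wipe and scrub jointly, and 0 give 4%. 9 + 3 + 1 + 0 = 13. The 4% figure occurs only in the listing of the one product. There are two readings:

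- *The listed product is the vaginal scrub.* The three sentences with 2% before the wipe or cloth can then refer to that item only, and they are consistent with the listing. One sentence conflicts: the allergy-risk sentence. It describes screening and does not specify the intervention.
- *The listed product is something else.* There is then no conflict between 2% and 4%. What remains is a listing that does not say what it is for, and a scrub with no product shown.

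The form (a brush or sponge rather than a cloth), and the statements that only one arm receives chlorhexidine, favour the first reading without proving it.

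**Consequences for screening.** The exclusion names chlorhexidine allergy with no strength attached, so 2% and 4% lead to the same eligibility decision.

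**Consequences for the statistics.** The planned size uses a control rate p1 = 0.20, a 40% relative reduction (p2 = 0.20 × 0.60 = 0.12), 80% power and a 0.05 level, taken as two-sided because the plan does not state sidedness. With mean rate (0.20 + 0.12)/2 = 0.16:

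n = [1.960·√(2·0.16·0.84) + 0.842·√(0.20·0.80 + 0.12·0.88)]² / 0.08²

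= [1.960·0.5185 + 0.842·0.5154]² / 0.0064 ≈ 2.102 / 0.0064 ≈ 328.5, which rounds up to 329.

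This reproduces the plan's 329 per group (power 80.1% at that size). No input refers to the agent or strength of the scrub, so reconciling the wording leaves the figure as it is.

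**The case for a change.** The best case for requiring a change is that the scrub is half of the experimental package and its strength cannot be read with certainty anywhere. Denying that the 4% product is the vaginal scrub does not rescue the text, because then no scrub product is shown at all. The word betadyne is in current text; it is neither a redaction nor superseded wording. A correction would cost little.

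Most of this is accurate as a description of the drafting. The Background phrase and the allergy-risk sentence do not fit the rest, and the product listing needs a label. It is too strong, though, to say that nothing settles the strength: the product listing may do so and merely fails to name its component.

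The step from loose wording to a defect in the plan does not stand. The scenario of a second agent in the active arm rests on the one phrase and runs against the arm definition, the title, the objective and three statements on the difference in care. Nothing in the documents suggests that products varied between participants. No number, endpoint or comparison depends on how the wording is resolved.

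**Conclusion.** No change to the plan follows. The betadyne phrase is most likely a clerical remnant in background text: 1 mention in 13, and absent from its near-twin in the Lay Summary. The strength question comes down to a product not labelled by component and, on one of two readings, a single risk sentence out of step with it. Read by its arm definitions, the protocol compares a chlorhexidine cloth plus chlorhexidine scrub, added to standard preparation, with standard preparation alone. The sample size, endpoints, analysis and eligibility rule as written stay the same.

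The Background sentence, the allergy-risk sentence and the product listing must still be reconciled as a matter of wording. Which agent and strength are intended is for the sponsor to state, and this review takes no position on that.

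The conclusion assumes that the active arm has no second antiseptic beyond standard preparation. If the sponsor were to say that it does, the chlorhexidine-only allergy exclusion and the statements on the sole difference in care would have to be reconciled with that, and the point would no longer be clerical. The consent pages are not among the documents, so their wording could not be compared.

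### Nothing makes randomization wait for a cesarean decision; if women are randomized earlier and analyzed by intention to treat, 400 per arm gives 80% power only if about 85–87% have a cesarean

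*Combined protocol and SAP*

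**What the plan says.** **Who is eligible, and when.** Inclusion Criteria: "The study will be offered to women at > 24 weeks gestation who are admitted in labor or admitted for induction of labor". Consent is taken on admission, and under Waiting Period for Obtaining Consent a woman "can still be consented to participate in the study at a later time in labor if not already delivered by cesarean section". At that stage cesarean is only a possibility. Risks to Subjects says: "The patients in our study are all consented to possible cesarean section upon admission for various indications".

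**When randomization follows.** How Participants will be screened: "If they meet eligibility criteria and chose to participate they will be randomized and receive care within the accepted standards". Provisions to Protect the Privacy Interests of Subjects, after describing the approach on admission: "If they choose to participate they will be randomized and receive care within the accepted standards". Description of the study design, directly after referring to women admitted to undergo labor: "The eligible women will be randomized to use of a 2% chlorhexidine gluconate (CHG) cloth and vaginal scrub".

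**What the sample size rests on.** Feasibility of Meeting Recruitment Goals, repeated under the study design, starts from about 1800 cesareans a year: "Of these, approximately 800 are cesarean sections after failed labor". It then assumes a 20% control rate and a 40% reduction, which gives 329 per group for 80% power, and adds: "We aim to recruit 400 patients per group (for a total of 800 patients) to account for patient drop out or non-compliance".

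**Analysis.** The Data Analysis Plan specifies intention to treat, with a chi-square or Fisher exact test at p<0.05. It does not restrict the analysis to women who had a cesarean. The only investigator withdrawal allowed is for a cesarean that becomes urgent; vaginal delivery is not mentioned.

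**The concern.** Two different trials fit this text. In one, women in labor are randomized when they agree to take part, and some later deliver vaginally. In the other, only women going to cesarean are randomized. The sample size suits only the second, while the sentences on randomization read more naturally as the first.

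If the first is what happens, women who deliver vaginally never receive the cloth or scrub, so the intervention cannot act on them. They nevertheless count in an intention-to-treat comparison and shrink the difference between arms. Restricting the analysis to cesareans avoids that dilution, but it leaves fewer women than calculated and is not the analysis set the plan names. The margin from 329 to 400 is already assigned to drop-out and non-compliance. A null result would then say little about the intervention, and more analysis after the data are in could not repair it.

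**Working it through.** **Inputs from the documents.** Control rate 20%; 40% relative reduction, so 12% in the active arm; 80% power; 329 calculated and 400 recruited per arm; significance at 0.05. Sidedness is not stated, but two-sided reproduces the plan's figure.

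**Inputs that are assumptions.**
- The share *f* of randomized women who have a cesarean. The documents give no count of labor admissions, so *f* cannot be derived and is varied.
- The infection rate *v* after vaginal birth, taken as equal in both arms. The Background puts infectious morbidity at 5–10% of cesareans, 5-fold higher than after vaginal delivery. Dividing 5–10% by 5 gives 1–2%; applying the same ratio to the 20% planning rate gives 4%. Hence *v* = 1% to 4%, with 0% as a check.

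**Step 1: the plan's own figure.** With p̄ = (p1 + p2)/2,

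n per arm = [1.960·√(2p̄(1−p̄)) + 0.842·√(p1(1−p1) + p2(1−p2))]² / (p1−p2)²

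For 20% versus 12%, p̄ = 0.16: (1.0162 + 0.4337)² / 0.08² = 328.5, so 329. The plan's figure is reproduced. Power is 80.1% at 329 per arm and 87.1% at 400.

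**Step 2: all randomized women analyzed.** The expected rates become

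control = 0.20*f* + *v*(1−*f*); active = 0.12*f* + *v*(1−*f*)

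The difference falls from 8 points to 8*f* points. At *f* = 40% it is 3.2 points: 8.6% versus 5.4% with *v* = 1% (power 42.6%), or 10.4% versus 7.2% with *v* = 4% (power 35.8%).

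**Step 3: cesareans only analyzed.** The rates stay at 20% and 12%, but only 400*f* women per arm remain.

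| Cesarean share *f* | Power, all randomized (*v* = 4% to 1%) | Power, cesareans only |
|---|---|---|
| 25% | 20–26% | 34% |
| 40% | 36–43% | 50% |
| 50% | 47–53% | 59% |
| 70% | 67–70% | 73% |
| 80% | 75–77% | 79% |
| 90% | 82–83% | 84% |

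Both columns use 400 per arm with no drop-out.

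**Step 4: break-even share for 80% power.**

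| | All randomized, *v* = 1% / 2% / 4% | Cesareans only |
|---|---|---|
| No drop-out (400 per arm) | 85.2% / 85.8% / 86.9% | 329/400 = 82% |
| Assumed 10% drop-out (360 per arm) | 92.9% / 93.2% / 93.7% | 329/360 = 91% |

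With *v* = 0% and no drop-out the all-randomized figure is 84.6%, so the result depends little on *v*. Exact binomial power of the chi-square test puts the break-even at about 84–87% for *v* from 0% to 4%.

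**Step 5: total N for 80% power, before drop-out.** Cesareans only: 2 × 329/*f* = 658/*f*, which is 1,645 at *f* = 40% and 940 at 70%. All randomized: 1,994–2,460 at 40% and 1,018–1,086 at 70%.

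**The case against.** Much of the text points to a cesarean-only trial. The title and objective are limited to cesarean after labor. In the Lay Summary and Background, the sentence on randomization follows one about patients undergoing cesarean section. The cloth and scrub are given before cesarean delivery, participation runs to six weeks after the procedure, and the data list is surgical. A target of 800 is natural as a count of cesareans when about 800 eligible ones occur each year over two years of enrollment. The missing withdrawal rule for vaginal delivery fits that reading equally well. On this view the defect is an unstated randomization time, not an underpowered trial. The power loss also needs a cesarean share below 82–87%, which the documents do not establish.

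Much of this stands. The likely intent may well be a cesarean cohort, the power figures are conditional, and the shares tabulated are illustrations. The plan also does not expressly label the 20% as the rate after post-labor cesarean. That is an inference from its placement and from the Background, which puts infection lower after vaginal birth and highest in cesareans after labor.

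An analysis restricted to women who reach cesarean might still be interpretable, because the intervention is given only at that point. However, participants are not blinded, the plan does not name that set, and below an 82% share it is too small.

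What does not stand is that the text settles the matter. The cesarean wording describes the target population and times the intervention; it does not time allocation. The sentences that place randomization put it after eligibility and agreement.

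**Conclusion.** The concern holds and must be fixed. The randomized population and the intention-to-treat set are undefined, and a team that followed the text could randomize women who then deliver vaginally.

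In that case, 400 per arm gives 80% power only if about 85–87% of randomized women have a cesarean, or 82% if only cesareans are analyzed. With 10% drop-out the requirements rise to 93–94% and 91%. These figures assume 20% versus 12% after cesarean, 1–4% after vaginal birth in both arms and no effect in women who deliver vaginally. They allow for no other non-compliance, so they are minimum shares.

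Confidence is high that the wording is missing. Whether there is an actual power deficit depends on when women are really randomized and on a cesarean share that the documents do not give. If randomization takes place at the cesarean decision, there is no loss from this source.

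**What to change.** 1. Keep consent at admission or later in labor. State under How Participants will be screened, Provisions to Protect the Privacy Interests of Subjects, and Description of the study design that randomization takes place only once cesarean has been decided.
2. In the sample-size text (Feasibility of Meeting Recruitment Goals and its repeat under the study design), count the 400 per group from that point. In the Data Analysis Plan, define the intention-to-treat set as all women so randomized.
3. Reconcile the exclusion of unplanned or emergency cesarean and the withdrawal for urgent cesarean with a target population of cesareans after failed labor, and with the chosen randomization point. How to resolve them is for the investigators; until they agree, it is unclear which women the 800 counts.
4. If randomization at admission is kept instead, state the expected cesarean share and the analysis set, and restate the power of 800 women or recompute N on that basis.

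Items 1 to 3 cost amended wording in those sections, and more women are consented than randomized. If allocation is now done at admission, the labor-floor workflow also changes, because the assignment is opened at the cesarean decision. The number randomized stays at 800. Item 4 would cost a larger N or a lower stated power.
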